#### Drug induced liver injury

Although rare, a potential for drug-induced liver injury (DILI) is under constant surveillance by sponsors and regulators. Therefore, this trial requires timely detection, evaluation, and follow-up of laboratory alterations in selected liver laboratory parameters to ensure subjects' safety; see also Section [5.2.6.1.5](#), adverse events of special interest.

#### **1.4.3      Overall assessment**

In summary, although not therapeutically tested in humans to date, BI 1358894 has the potential to become an oral treatment for as an adjunct to therapy and for the treatment of . Based upon preclinical data for BI 1358894, the preliminary clinical data from the on-going FIH study, as well as the implemented safety measures described above, healthy subjects will not be exposed to undue risks in relation to the important information expected from this trial as a basis for further clinical development of this compound. Healthy volunteers are not expected to have any direct benefit from participation in the clinical trial with BI 1358894, as is the usual case in such Phase I trials. Considering the medical need for the development of a safer and more effective treatment for patients with disorders, the Sponsor considers that the benefit outweighs the potential risks and justifies exposure of healthy human volunteers.

## **2. TRIAL OBJECTIVES AND ENDPOINTS**

### **2.1 MAIN OBJECTIVES, PRIMARY AND SECONDARY ENDPOINTS**

#### **2.1.1 Main objectives**

The main objectives of this trial are to investigate safety, tolerability and pharmacokinetics (PK) of BI 1358894 in healthy male subjects following oral administration of single rising doses.

#### **2.1.2 Primary endpoint**

The primary endpoint for assessment of safety and tolerability of BI 1358894 is the number [N(%)] of subjects with drug related adverse events.

#### **2.1.3 Secondary endpoint**

The following pharmacokinetic parameters will be determined for BI 1358894 if feasible:

- $AUC_{0-tz}$  (area under the concentration-time curve of the analyte in plasma over the time interval from 0 to the last quantifiable data time point  $t_z$ )
- $AUC_{0-\infty}$  (area under the concentration-time curve of the analyte in plasma over the time interval from 0 extrapolated to infinity)
- $C_{max}$  (maximum measured concentration of the analyte in plasma)

Proprietary confidential information © 2019 Boehringer Ingelheim International GmbH or one or more of its affiliated companies

### 3. DESCRIPTION OF DESIGN AND TRIAL POPULATION

#### 3.1 OVERALL TRIAL DESIGN AND PLAN

This single-rising dose trial is designed as double-blind, randomised, and placebo-controlled within parallel dose groups.

It is planned to include a total of 24 healthy male subjects in the trial. The subjects will be assigned to 3 groups consisting of 8 subjects per group; the groups will be dosed sequentially (see Table 3.1: 1).

The trial design is depicted in Figure 3.1: 1.

[figure not shown]

Figure 3.1: 1

Overview of trial design

Within each dose group, 6 subjects will receive BI 1358894 and 2 will receive placebo. Only one dose is tested within each dose group.

Proprietary confidential information © 2019 Boehringer Ingelheim International GmbH or one or more of its affiliated companies

The dose groups to be evaluated are outlined in Table 3.1: 1 below.

Table 3.1: 1

Dose groups

Dose Group	1	2	3
Dose (mg)	50	100	200
Number of subjects	8	8	8
Subjects receiving placebo	2	2	2
Subjects receiving active drug	6	6	6

The groups will be dosed consecutively in ascending order, and a time interval of at least 6 days will be maintained between the last drug administration to subjects in the previous dose group and the first drug administration to subjects in the subsequent dose group. The decision to treat the next dose group will be based upon safety, and tolerability data of all the preceding dose groups. The next dose group will only be treated if, in the opinion of the investigator, no safety concerns have arisen in the preceding dose groups (i.e. no dose-limiting events occurred), and if none of the pre-specified trial-specific stopping criteria have been met (refer to Section [3.3.4](#)). For safety reasons, Dose Group 3 will be divided into 2 cohorts (per cohort: 3 subjects on active and 1 subject on placebo, treated in parallel). Both cohorts will be dosed in a randomised fashion.

A documented safety review must take place prior to each dose escalation. Furthermore, an unscheduled safety review meeting can be requested anytime by the Principal Investigator (or an authorised deputy) or the sponsor of the study (for instance, due to the occurrence of any unforeseen adverse events).

Although no formal Safety Review meeting will take place within a given dose group, safety will be continuously monitored during this trial, and an individual will only be dosed in the absence of any safety concern (i.e. no dose-limiting events occurred) and if none of the pre-specified trial-specific stopping criteria have been met (refer to Section 3.3.4).

The minimum data set for review consists of the following:

- AEs in the current and preceding dose groups including clinically relevant findings from ancillary safety testing listed below (Note: AEs may be ongoing at the time of Safety Reviews and AE information may be subject to change prior to Database Lock)
- Results from 12-lead ECG in the current and preceding dose groups
- Vital signs in the current and preceding dose groups
- Clinical laboratory tests in the current and preceding dose groups
- Check of criteria for stopping subject treatment as per Section [3.3.4.1](#)

The decision to escalate the dose will be made jointly by the Principal Investigator (or an authorised deputy) and the Clinical Trial Leader (or an authorised deputy) after in-depth analysis of all available safety data, especially SAEs (if occurred), AEs, and out-of-range laboratory results (if considered clinically significant). Dose escalation will only be permitted

Proprietary confidential information © 2019 Boehringer Ingelheim International GmbH or one or more of its affiliated companies

if no safety concerns exist neither in the opinion of the Principal Investigator (or an authorised deputy) nor the Clinical Trial Leader (or an authorised deputy).

Safety Reviews can be conducted face-to-face or by video/telephone conference. The Clinical Trial Leader is responsible for the organisation and minutes of the reviews. Minutes will be signed off by the Principal Investigator (or an authorised deputy) and Clinical Trial Leader (or an authorised deputy), and will be filed in the investigator site file (ISF) and trial master file (TMF).

An overview of all relevant trial activities is provided in the [Flow Chart](#). For visit schedules and details of trial procedures at selected visits, refer to Sections [6.1](#) and [6.2](#), respectively.

### **3.2 DISCUSSION OF TRIAL DESIGN, INCLUDING THE CHOICE OF CONTROL GROUP**

For single-rising dose trials, the sequential rising dose design described in Section [3.1](#) is viewed favourably under the provision not to expose the subjects involved to undue risks since the main study objective is to investigate safety and tolerability of BI 1358894.

With the rising dose design, double-blind conditions regarding the subject's treatment (active or placebo) are maintained within each dose group. However, subjects and investigators will be aware of the dose of drug administered. The disadvantage of the trial design is a possible observer bias with regard to the dose-dependent effects; in addition, the sequential dosing of groups could potentially result in time-related effects. However, as such effects are expected to be small relative to the differences between the doses in the broad range investigated, unbiased comparisons between treatments can still be expected.

It is standard in single or multiple rising dose trials involving healthy volunteers to include a placebo group to control for safety and tolerability of the trial medication. Each dose group consists of 8 subjects, with 6 on active treatment, and 2 on placebo. For data analysis purposes, the placebo control group will include all subjects of all dose groups treated with placebo. Six subjects per active treatment group are generally considered to be sufficient for the exploratory evaluation of pharmacokinetics.

### **3.3 SELECTION OF TRIAL POPULATION**

It is planned that 24 healthy male will enter the study. Subjects will be recruited from the volunteers' pool of the trial site.

Only male subjects will be included in the trial because no data on reproductive toxicology are available at this time.

A log of all subjects enrolled into the trial (i.e. who have signed informed consent) will be maintained in the ISF irrespective of whether they have been treated with investigational drug or not.

#### **3.3.1 Main diagnosis for trial entry**

The study will be performed in healthy subjects.

### **3.3.2 Inclusion criteria**

Subjects will only be included in the trial if they meet the following criteria:

1. Healthy male subjects according to the assessment of the investigator, as based on a complete medical history including a physical examination, vital signs (BP, PR), 12-lead ECG, and clinical laboratory tests
2. Japanese ethnicity, according to the following criteria:
  - born in Japan, have lived outside of Japan <10 years, and have parents and grandparents who are Japanese
3. Age of 20 to 45 years (inclusive) at screening
4. BMI of 18.5 to 25.0 kg/m^2 (inclusive) at screening
5. Signed and dated written informed consent prior to admission to the study, in accordance with Good Clinical Practice (GCP) and local legislation
6. Willingness to comply with contraception requirements. Subjects who are sexually active must use with their female partner, adequate contraception throughout the study and until three months after the last administration of trial medication. Adequate methods are:
  - A vasectomy performed at least 1 year prior to screening (with medical assessment of the surgical success) or
  - Surgical sterilisation (including bilateral tubal occlusion, hysterectomy or bilateral oophorectomy) of the subject's female partner or
  - The use of condoms, if the female partner uses an adequate contraception method in addition, e.g., intrauterine device (IUD), hormonal contraception (e.g., implants, injectables, combined oral or vaginal contraceptives) that started at least 2 months prior to first drug administration, or barrier method (e.g., diaphragm with spermicide)

Unprotected sexual intercourse with a pregnant female partner is not allowed throughout the study and until three months after the last administration of trial medication.

### **3.3.3 Exclusion criteria**

Subjects will not be allowed to participate, if any of the following general criteria apply:

1. Any finding in the medical examination (including BP, PR or ECG) deviating from normal and assessed as clinically relevant by the investigator
2. Repeated measurement of systolic blood pressure outside the range of 90 to 140 mmHg, diastolic blood pressure outside the range of 50 to 90 mmHg, or pulse rate outside the range of 50 to 90 bpm
3. C-Reactive Protein (CRP) > upper limit of normal (ULN), erythrocyte sedimentation rate (ESR)  $\geq$  15 millimeters/hour, liver and kidney parameter above ULN, other laboratory value outside the reference range that the investigator considers to be of clinical relevance
4. Any evidence of a concomitant disease assessed as clinically relevant by the investigator
5. Gastrointestinal, hepatic, renal, respiratory, cardiovascular, metabolic, immunological or hormonal disorders
6. Cholecystectomy or other surgery of the gastrointestinal tract that could interfere with the pharmacokinetics of the trial medication (except appendectomy or simple hernia repair)

Proprietary confidential information © 2019 Boehringer Ingelheim International GmbH or one or more of its affiliated companies

7. Diseases of the central nervous system (including but not limited to any kind of seizures or stroke), and other relevant neurological or psychiatric disorders
8. History of relevant orthostatic hypotension, fainting spells, or blackouts
9. Chronic or relevant acute infections including viral hepatitis, human immunodeficiency virus (HIV) and/or syphilis. (Subject with positive Hepatitis B core antibody will not be allowed to participate in this trial)
10. History of relevant allergy or hypersensitivity (including allergy to the trial medication or its excipients)
11. Use of drugs within 30 days of planned administration of trial medication that might reasonably influence the results of the trial (including drugs that cause QT/QTc interval prolongation)
12. Intake of an investigational drug in another clinical trial within 60 days of planned administration of investigational drug in the current trial, or concurrent participation in another clinical trial in which investigational drug is administered
13. Smoker (more than 10 cigarettes or 3 cigars or 3 pipes per day)
14. Inability to refrain from smoking on specified trial days
15. Alcohol abuse (consumption of more 30 g per day for males)
16. Drug abuse or positive drug screening
17. Blood donation of more than 400 mL within 12 weeks or 200 mL within 30 days or plasma donation within 2 weeks prior to administration or intended blood donation during the trial
18. Intention to perform excessive physical activities within one week prior to the administration of trial medication or during the trial
19. Inability to comply with the dietary regimen of the trial site
20. A marked baseline prolongation of QT/QTc interval (such as QTc intervals that are repeatedly greater than 450 ms) or any other relevant ECG finding at screening
21. A history of additional risk factors for *Torsade de Pointes* (such as heart failure, hypokalaemia, or family history of Long QT Syndrome)
22. Subject is assessed as unsuitable for inclusion by the investigator, for instance, because the subject is not considered able to understand and comply with study requirements, or has a condition that would not allow safe participation in the study

In addition, the following trial-specific exclusion criteria apply:

23. Any lifetime history of suicidal behaviour (i.e. actual attempt, interrupted attempt, aborted attempt, or preparatory acts or behaviour)
24. Any suicidal ideation of type 2 to 5 on the C-SSRS in the past 12 months (i.e. active suicidal thought, active suicidal thought with method, active suicidal thought with intent but without specific plan, or active suicidal thought with plan and intent)

For study restrictions, refer to Section [4.2.2](#).

Proprietary confidential information © 2019 Boehringer Ingelheim International GmbH or one or more of its affiliated companies

### **3.3.4 Withdrawal of subjects from treatment or assessments**

Subjects may discontinue trial treatment or withdraw consent to trial participation as a whole ('withdrawal of consent') with very different implications; please see sections 3.3.4.1 and [3.3.4.2](#) below.

If a subject is removed from or withdraws from the trial prior to the first administration of trial medication, the data of this subject will not be entered in the case report form (CRF) and will not be reported in the clinical trial report (CTR). If a subject is removed from or withdraws from the trial after the first administration of trial medication, this will be documented and the reason for discontinuation must be recorded in the CRF; in addition, the data will be included in the CRF and will be reported in the CTR.

At the time of discontinuation, a complete end of trial examination will be performed, if possible, and the information will be recorded in the CRF. If the discontinuation occurs before End of Trial (EOT) visit, the discontinued subject should if possible be questioned for AEs and concomitant therapies in order to ensure collection of AEs and concomitant therapies until the planned EOT visit date, if not contrary to any consent withdrawal of the subject.

#### **3.3.4.1 Discontinuation of trial treatment**

An individual subject will discontinue trial treatment if:

1. The subject wants to discontinue trial treatment, without the need to justify the decision
2. The subject has repeatedly shown to be non-compliant with important trial procedures and, in the opinion of both, the investigator and sponsor representative, is not willing or able to adhere to the trial requirements in the future
3. The subject needs to take concomitant medication that interferes with the investigational medicinal product or other trial treatment
4. The subject can no longer receive trial treatment for medical reasons (such as surgery, adverse events [AEs], or diseases)
5. An AE or clinically significant laboratory change or abnormality occurs that the investigator assesses as warranting discontinuation of treatment. This may include cases of sustained symptomatic hypotension (BP <90/50 mmHg) or hypertension (BP >180/100 mmHg), clinically relevant changes in ECG requiring intervention, or unexplained hepatic enzyme elevations at any time during the trial
6. The subject has an elevation of AST and/or ALT  $\geq$ 3-fold ULN combined with an elevation of total bilirubin  $\geq$ 2-fold ULN (measured in the same blood sample), or ALT and/or AST elevations  $\geq$ 10 fold ULN and/or needs to be followed up according to the DILI checklist provided in the ISF
7. The subject shows a raised CRP level of  $>3.00$  mg/dL or an Erythrocyte Sedimentation Rate (ESR) of  $\geq$  20 millimeters/hour.

In addition to these criteria, the investigator may discontinue subjects at any time based on his or her clinical judgment.

Proprietary confidential information © 2019 Boehringer Ingelheim International GmbH or one or more of its affiliated companies

A subject can also be removed from the trial if eligibility criteria are being violated.

Even if the trial treatment is discontinued, the subject remains in the trial and, given his/her agreement, will undergo the procedures for early treatment discontinuation and follow up as outlined in the [Flow Chart](#) and section [6.2.3](#).

### **3.3.4.2 Withdrawal of consent to trial participation**

Subjects may withdraw their consent to trial participation at any time without the need to justify the decision. If a subject wants to withdraw consent, the investigator should be involved in the discussion with the subject and explain the difference between trial treatment discontinuation and withdrawal of consent to trial participation, as well as explain the options for continued follow up after trial treatment discontinuation, please see section [3.3.4.1](#) above

### **3.3.4.3 Discontinuation of the trial by the sponsor**

Boehringer Ingelheim reserves the right to discontinue the trial at any time for any of the following reasons:

1. Failure to meet expected enrolment goals
2. New toxicological findings, serious adverse events, or any safety information invalidating the earlier positive benefit-risk assessment. Dose escalation will be terminated if more than 50% of the subjects at one dose level show drug-related and clinically relevant adverse events of moderate or severe intensity, or if at least one drug-related serious adverse event is reported.
3. Violation of GCP, or the CTP (clinical trial protocol), or the contract with BI impairing the appropriate conduct of the trial.
4. The sponsor decides to discontinue the further development of the investigational product
5. Dose escalation will be stopped if at least 2 subjects on active treatment at one dose level have relevant individual QT prolongations, i.e. a QTc increase of greater than 60 ms from baseline in connection with absolute QT or QTc greater than 500 ms, as confirmed by a repeat ECG recording
6. Dose escalation will be stopped if at least 2 subjects at one dose level showed a sustained decrease in systolic blood pressure of  $\geq 20$  mmHg for at least 2 hours after drug administration compared to baseline (Day 1, predose) which will be measured after 15 min in supine position (to avoid false positive signals because of the required prolonged resting period after drug intake).

The investigator / trial site will be reimbursed for reasonable expenses incurred in case of trial termination (except if item 3 applies).

### **3.3.5 Replacement of subjects**

If some subjects do not complete the trial, the Clinical Trial Leader together with the Trial Pharmacokineticist and the Trial Statistician are to decide, if and how many subjects will be replaced. A replacement subject will be assigned a unique trial subject number, and will be assigned to the same treatment as the subject replaces.

## **4. TREATMENTS**

### **4.1 INVESTIGATIONAL TREATMENTS**

The investigational products have been manufactured by BI Pharma GmbH & Co. KG.

#### **4.1.1 Identity of the Investigational Medicinal Products**

The characteristics of the test product are given below:

Substance:

BI 1358894

Pharmaceutical formulation:

Film-coated tablet

Source:

BI Pharma GmbH & Co. KG, Germany

Unit strength:

25 mg, 100 mg

Posology:

2-0-0 (50 mg), 1-0-0 (100 mg), and 2-0-0 (200 mg)

Route of administration:

oral

Duration of use:

Single dose

The characteristics of the reference product (placebo) are given below:

Substance:

Matching placebo

Pharmaceutical formulation:

Film-coated tablet

Source:

BI Pharma GmbH & Co. KG, Germany

Unit strength:

n.a.

Posology:

2-0-0 (50 mg), 1-0-0 (100 mg), and 2-0-0 (200 mg)

Route of administration:

oral

Duration of use:

Single dose

#### **4.1.2 Selection of doses in the trial**

The dose range of BI 1358894 for this trial was selected on the basis of the data obtained in the ongoing FIH SRD Trial 1402-0001. So far, dose levels up to 200 mg in fasting status and 100 mg in fed status were well tolerated.

The doses selected for this trial cover the estimated therapeutic range and supra-therapeutic range and include a safety margin (see Section [1.2](#)).

#### **4.1.3 Method of assigning subjects to treatment groups**

Prior to the screening visit, subjects will be contacted in writing and informed about the planned visit dates. The subjects willing to participate will be recruited to dose groups according to their temporal availability. As soon as enough subjects are allocated to 1 of the 3

Proprietary confidential information © 2019 Boehringer Ingelheim International GmbH or one or more of its affiliated companies

dose cohorts, the following subjects will be allocated to one of the other dose cohorts. Therefore, the allocation of subjects to dose cohorts is not influenced by trial personnel, but only by the subjects' temporal availability. Because the study includes healthy subjects from a homogenous population, relevant imbalances between the dose groups are not expected.

Subjects will be assigned to treatments (active treatment or placebo) prior to the first administration of trial medication. For this purpose, the randomisation list will be provided to the trial site in advance. Numbers of the randomization list will be allocated to subjects by the method 'first come first served'. Subjects are then assigned to treatment according to the randomisation list. Once a subject number has been assigned, it cannot be reassigned to any other subject.

The randomisation procedure is described in Section [7.6](#).

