#### **4.1.5 Blinding and procedures for unblinding**

##### **4.1.5.1 Blinding**

The trial is designed double-blind. The treatments administered (active or placebo) will be blinded to the subjects and the investigators (outcome assessors) in order to limit the occurrence of any bias which the knowledge of treatment may have.

Regarding the sponsor, the database of this trial will be handled open label. This means that trial functions of the sponsor are unblinded (including clinical trial leader, data manager, statistician, bioanalyst, pharmacokineticist, pharmacometrist, drug metabolism scientist as well as dedicated contract research organization (CRO) personnel). The objective of the trial is not expected to be affected.

Within the central ECG lab, the staff involved with interval will be blinded with respect to the treatment and also with regard to the recording date and time as well as planned time points of the ECGs. The interval measurements for a given subject will be performed in a random and blinded sequence by a single technician.

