##### **4.1.5.2 Unblinding and breaking the code**

The investigator or designee will be supplied with a set of sealed envelopes containing the medication codes for each subject according to the randomisation scheme. The envelopes will be kept unopened at the trial site until the end of data collection. An envelope may only be opened in emergency situations when the identity of the trial drug must be known to the investigator in order to provide appropriate medical treatment or otherwise assure safety of trial participants. If the envelope for a subject is opened, the sponsor must be informed

Proprietary confidential information © 2019 Boehringer Ingelheim International GmbH or one or more of its affiliated companies

immediately. The reason for breaking the code must be documented on the envelope and/or appropriate CRF page along with the date and the initials of the person who broke the code.

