## **7.6 RANDOMISATION**

Subjects will be randomised within each dose group in a 3:1 ratio (test treatment to placebo).

The sponsor will arrange for the randomisation as well as packaging and labelling of trial medication. The randomisation list will be generated using a validated system that uses a pseudo-random number generator and a supplied seed number so that the resulting allocation is both reproducible and non-predictable.

The randomisation list will contain additional blocks to allow for subject replacement (refer to Section [3.3.5](#)).

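### Does sending the randomisation list to the trial site in advance (Protocol 4.1.3) undo the double blind?

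*Protocol*

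**What the plan says.** Section 4.1.3 of the Protocol covers assignment to active treatment or placebo before dosing. It states: "For this purpose, the randomisation list will be provided to the trial site in advance". Numbers from the list go to subjects in order of arrival, and then: "Subjects are then assigned to treatment according to the randomisation list". For the procedure it refers to Section 7.6.

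Section 7.6 describes a list generated by a validated system from "a supplied seed number so that the resulting allocation is both reproducible and non-predictable". It also says: "The sponsor will arrange for the randomisation as well as packaging and labelling of trial medication".

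The blinding rules are in Section 4.1.5:

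- Section 4.1.5.1: "The treatments administered (active or placebo) will be blinded to the subjects and the investigators (outcome assessors". The unblinded functions it lists are on the sponsor's side, with dedicated CRO personnel. No site role is named.
- Section 4.1.5.2: the site receives each subject's medication code in a sealed envelope. "The envelopes will be kept unopened at the trial site until the end of data collection", except where an emergency requires the treatment to be known.

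Section 3.2 says that "double-blind conditions regarding the subject's treatment (active or placebo) are maintained within each dose group", while subjects and investigators do know the dose. The SAP says nothing about access to the list.

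**The concern.** Section 7.6 uses the term randomisation list for the document that holds the allocation, and Section 4.1.3 uses the same term for what is sent to the site. Neither section distinguishes a masked site copy from the list that carries the treatments, and neither says who may hold or read it. Taken alone, Section 4.1.3 could mean that the site holds an open key to active and placebo. That would sit badly with investigator blinding, with sealed envelopes and with the double-blind claim in Section 3.2.

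The stakes would be real. The primary endpoint "is the number [N(%)] of subjects with drug related adverse events", and Section 5.2.6.1.7 leaves relatedness to medical judgment. Because the dose is known within each group, the active/placebo blind is the only masking left for that judgment at the site. The same judgment enters the escalation rules in Section 3.3.4.3, and under Section 3.1 the Principal Investigator shares the escalation decision. An open list could also let enrolling staff foresee the next assignment.

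**Working it through.** **The plan's own figures.** Section 3.1 gives 3 dose groups of 8 subjects, each with 6 on active drug and 2 on placebo.

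- Total: 3 × 8 = 24, as stated in Section 7.7.
- Active: 3 × 6 = 18. Placebo: 3 × 2 = 6. Ratio 18:6 = 3:1, as stated in Section 7.6.

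**What an open list would reveal.**

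- A dose group of 8 with 2 on placebo has C(8,2) = 28 possible sequences.
- If Dose Group 3 is randomised as its two cohorts of 3 active and 1 placebo, there are 4 × 4 = 16.
- An open list reduces either number to one known sequence. A numbers-only list leaves both unchanged.

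**Weight of one subject in the primary endpoint.**

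- In one active dose group, or in pooled placebo: 1/6 = 16.7 percentage points.
- In the SAP's total over all BI 1358894 subjects (SAP Section 6.1): 1/18 = 5.6 percentage points.

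These weights apply to any reclassified subject in a trial of this size, whatever the cause. They do not measure an effect of the wording in Section 4.1.3.

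**Which kind of list fits the protocol?** No arithmetic decides this, so the passages have to be set side by side.

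1. *Section 4.1.3 itself.* What is handed out is a number from the list. A subject who gets the next number and the pack bearing it has been assigned according to the list, and nobody at the site needs to read a treatment.
2. *Section 7.6.* The sponsor arranges packaging and labelling as well as randomisation, so number and contents can be linked before the medication reaches the site.
3. *Sections 4.1.1 and 4.1.4.* Placebo is a matching film-coated tablet, given in the same number of units as the active dose. The site does not need the code to prepare a dose.
4. *Section 4.1.8.* Accountability records at the site use code numbers for the product and for the subjects, which suits medication handled by number.
5. *Section 4.1.5.2.* One sealed code per subject has a purpose only if the site does not already hold the codes openly.
6. *Section 3.3.5.* A replacement subject receives the treatment of the subject replaced. The Clinical Trial Leader, Trial Pharmacokineticist and Trial Statistician decide on replacement, and Section 4.1.5.1 lists those functions as unblinded. This step does not require an open list at the site either.

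All six fit a numbers-only list. An open list that assessors can read contradicts the fifth and breaks Section 4.1.5.1.

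**The case for a change.** The best case for a change is that Section 4.1.3 is the operative instruction for assignment, and site staff follow the text in front of them. It uses the same term as Section 7.6, and masking has to be inferred from other sections. No redaction in Sections 4.1.3, 4.1.5 or 7.6 explains the silence, and no unblinded site role is named who could properly hold a decoded copy. Saying outright that the copy carries no treatment codes would take about two sentences and no extra staff.

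Part of this stands. The omission is real, and the protocol would be clearer with the point stated.

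It does not follow that the plan permits unblinding. Showing treatment codes to an outcome assessor is barred by Section 4.1.5.1 wherever the list is kept, and the envelope procedure is already the stated way to break the code at the site. If a literal reading of one sentence collides with an explicit rule two sections later, the protocol taken as a whole forbids that reading.

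The missing site role is weak evidence as well, because the roles in Section 4.1.5.1 are given as examples on the sponsor's side. Packing and label details are left to the investigator site file (Section 4.1.6), and tasks and functions to the sponsor's procedures (Section 8.7). Rules for handling the list may be there. The documents do not show this, but it limits what can be read into the protocol's silence.

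**Conclusion.** This is a gap in wording that a sponsor and site following the whole protocol would fill in the blinded way. The documents do not show that anyone would be unblinded, and their explicit rules forbid it for investigators.

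Its size cannot be stated as a bias. If the site copy carries numbers only, 0 of the 24 allocations are exposed. If it carried codes that assessors could read, all 24 would be, but that would breach Section 4.1.5.1 and could not be called following the plan. The sample size, analysis sets and descriptive analyses are the same with or without a clarifying sentence. No hypothesis is tested (Section 7.2), and adverse events are also tabulated regardless of causality (SAP Section 7.8.1).

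The conclusion rests on two assumptions: that Sections 4.1.3, 4.1.5 and 7.6 are applied together, and that the medication is labelled by number, as Section 4.1.8 suggests. Recording that the site list carries no treatment codes would be harmless, but no result depends on it, so the plan does not need to change.
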